Based upon published reports, we anticipate that participants in the intervention arm of the study will experience a health benefit; they will be less likely to acquire TD while abroad. They also may benefit, in the event that they do acquire TD, by having a shorter duration and lesser severity of TD symptoms in comparison to those in the placebo group.

Description of the Potential Risks to Anticipated Benefit Ratio

The potential benefits of participating in this study outweigh the minimal risks.

Emergency Care

We do not anticipate participants needing emergency care as a part of this study.

Participants will be provided phone and email contact information for study personnel in the event questions or concerns arise that may relate to their participation in the study.

Study Timeline

Table 1. Study Timeline, 2017–2020

Study Component	Date of Anticipated Start	Date of Anticipated End
Protocol Writing and Coordination	March 2017	October 2017
Submission of protocol/consent forms for IRB approval	November 2017	Late December 2017
Training of study personnel	January 2018	January 2018
Enrollment of participants	February 2018	July 2019
Laboratory analysis of stool specimens	February 2018	October 2019
Data entry	February 2018	October 2019
Data analysis (every 3 months)	April 2018	November 2019
Manuscript writing and clearance	November 2019	March 2020
Dissemination of findings	March 2020	

Study Population

Description and Source of the Study Population

Participants will be selected from persons seeking a pre-travel consultation at The New York Center for Travel and Tropical Medicine, New York, United States. This clinic serves travelers by providing pre-travel consultative services, in addition to post-travel screening, assessment, diagnostic, and treatment services. Centrally located in Manhattan, this clinic serves a large variety of international travelers, including tourists, immigrants or their relatives, and business travelers, among others. Travelers' destinations are equally varied, reflecting the ethnic and cultural diversity of New York City.

Definitions

Diarrhea:

≥ 3 unformed stools in 24 hours, with or without associated symptoms such as fever, cramping, or abdominal pain

Travelers' diarrhea:

Diarrhea that begins while traveling (after arrival in a country) or within 10 days after return

Study period:

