Includes the 7 days prior to departure in which the pre-travel questionnaire and a biologic (stool) specimen is collected, the full duration of travel, and through 10 days maximum post-return from travel, or until both the post-travel questionnaire and submission of the post-travel biologic (stool) specimen is complete (a maximum of 17 days post-travel)

Travel companion (group):

Two or more study participants with a common relation (friends, colleagues, or relatives) with the same itinerary, who anticipate performing the same activities during travel

Trip duration:

The number of days spent in country; excludes air travel time

Severe TD:

Hospitalization to an inpatient ward either during travel or after travel with a diagnosis of diarrhea

Acquisition of AMR gene(s):

The presence in a post-travel biologic (stool) specimen of one or more antimicrobial resistance gene(s) that were not present in a pre-travel biologic (stool) specimen from the same person, and which is known to confer antimicrobial resistance to one or more antimicrobial agents ("resistome")

Medication compliance:

Full = participant takes all scheduled doses according to directions

Good = If <15% of BSS or placebo doses were missed during travel

Fair = If 15–30% of BSS or placebo doses were missed during travel

Poor = If >30% of doses were missed during travel

Questionnaire compliance:

Full = participant completes all questionnaires

Good = participant completes >80% of all during travel questionnaires, AND
both the pre- and post-travel questionnaires

Fair = participant completes between 30–80% of all during travel
questionnaires, including AT LEAST the pre-travel questionnaire

Poor = participant completes <40% of all during travel questionnaires, and AT
LEAST the pre-travel questionnaire

Biologic (stool) specimen compliance:

Full = BOTH specimens collected and sent

Fair = ONLY one specimen collected and sent

Poor = No specimens collected and sent

Loss to follow-up:

Failure to complete the post-travel questionnaire after three attempts to contact the participant or if submission of the post-travel biologic specimen (stool) occurs more than 10 days after return from travel or is not submitted

Participant Inclusion Criteria

Willing participants must meet the inclusion criteria as outlined here:

1. Be ≥ 18 and <70 years of age at the time of enrollment

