Participants will be asked to submit a web-based post-travel questionnaire within 10 days after return from travel, submit a biologic (stool) specimen, and provide all daily questionnaires that were completed during travel. This will be submitted via a pre-paid envelope addressed to the study clinic that was given to the participant when enrolled.

Study personnel will make follow-up telephone calls on days 3, 5, 7, and 10 after return as needed to encourage that the post-travel questionnaire, paper questionnaires from during-travel, and biologic (stool) specimens are all submitted.

The web-based post-travel questionnaire will include questions on:

1. The development of symptoms of TD since returning from abroad, including duration of symptoms
2. New antibiotic or other medication use
3. Adverse events

4. Contact with healthcare facilities or providers
5. Changes to travel itinerary during travel

Table 2. Schedule of CLINIC events (primary and secondary objectives):

	Stages			
	Pre-travel consultation (baseline)	Pre-travel (≤ 7 days before departure)	During travel	Post-travel (≤ 10 days after return)
Screening Questionnaire	X			
Informed Consent	X			
Pre-travel Questionnaire*		X		
Follow-up call(s)		X		X [†]
During travel Questionnaires			X	
Post-travel Questionnaire				X
Adverse Events Reporting			X	X

*Study personnel will call the participant to complete a pre-travel questionnaire 7 days before departure and to ensure that answers to the questions on the screening questionnaire have not changed. Reminder calls will occur as per **APPENDIX G**. If the traveler is leaving exactly 7 days after the pre-travel consultation/enrollment visit, this questionnaire can be performed at the pre-travel consultation/enrollment visit.

[†]Study personnel will call the participant within 3 days of return from travel to remind participants to complete their web-based post-travel questionnaire, submit any paper during travel questionnaires, and collect and submit the post-travel biologic (stool) sample. Reminder calls will occur as per **APPENDIX G**.

Laboratory Instruments

All participants will collect and submit a fresh biologic (stool) sample in the 7 days before departure and within 10 days after return. Participants will be

provided all instructions and materials necessary to collect and submit these samples at enrollment. All biologic (stool) specimens will be submitted by mail, and participants will be given pre-paid shipping materials.

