Headache	
Dizziness	
Ringing in your ears	
Muscle pain/soreness	
Joint pain/swelling/redness	

Drowsiness (severe)	
Confusion	
Depression	
Other (list/describe):	
Medical care	
Did you seek medical care for one or more of these symptoms? (Yes/No/Don't Know)	Y N D
→ If yes, where? (check the corresponding box(es))	...
A doctor's office	
Urgent care clinic (outpatient)	
Emergency room	
Hospital outpatient clinic setting	
Hospital inpatient ward – hospitalized	
Other (specify)	
→ Was your diagnosis travelers' diarrhea? (Yes/No/Don't Know)	Y N D
Have you started any medications in the past 24 hours? (Yes/No/Don't Know)	
→ If yes, what medication(s)?	
→ Please circle those that were provided for you at your pre-travel consultation with the study clinic.	...
What city(ies) and country(ies) have you been in during the past 24 hours? Please write answers to all questions in the corresponding box.	
Have you eaten any of the following in the past 24 hours? (Yes/No/Don't Know)	
→ Fermented or pickled foods (e.g., bean paste, fish kimchi, etc.)	Y N D
→ Yogurt	Y N D
Comments:	

Post-travel Questionnaire

PARTICIPANT UNIQUE ID: _____

GROUP ID: _____

1. Have you had any of the following symptoms since returning home from your trip (circle all that apply)?

Symptom	Duration (in days)
Fever	
Nausea	
Vomiting	
Loose stools (less than three in a 24 hour period)	
Diarrhea (three or more loose stools in 24 hours)	
Bloody diarrhea	
Constipation	
Dark or black stool	
Dark or black tongue	
Abdominal pain	
Abdominal cramps	
Fecal urgency	
Bloating	
Flatulence/gas	
Congestion/runny nose	
Sore throat	
Cough	
Rash	
Headache	
Dizziness	
Ringing in your ears	
Muscle pain/soreness	
Joint pain/swelling/redness	
Drowsiness (severe)	
Confusion	
Depression	
Other (list/describe):	
Don't know	...
I would rather not answer	...

2. Did you start taking any of the following medications since you arrived home (circle all that apply)?

- a. **Oral or intravenous (IV) antibiotics** (e.g., azithromycin [Zithromax], ciprofloxacin [Cipro], rifaximin [Xifaxan], doxycycline or minocycline, metronidazole [Flagyl], cotrimoxazole [Bactrim or Septra], penicillins [e.g., amoxicillin, Augmentin], or cephalosporins [e.g., Keflex])

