APPENDIX G: Follow-up Phone Call Schedule

	7 days before travel	5 days before travel	3 days before travel	1 day before travel
Review all screening questionnaire answers with the participant, perform the pre-travel questionnaire, and provide a reminder for stool sample submission	X	X	X	X
	3 days after travel	5 days after travel	7 days after travel	10 days after travel
Reminder for post-travel questionnaire and stool sample submission	X	X	X	X

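### TD counts up to day 10 after return, but the only post-return symptom form may be answered earlier and no later scheduled contact asks about symptoms

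*Combined protocol and SAP*

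**What the plan says.** - **Endpoint window** (Definitions, Travelers' diarrhea): "Diarrhea that begins while traveling (after arrival in a country) or within 10 days after return".
- **Post-return form** (Study Instruments, Post-travel): "Participants will be asked to submit a web-based post-travel questionnaire within 10 days after return from travel". A latest day is set; an earliest day is not.
- **What it asks** (Appendix E, question 1): "Have you had any of the following symptoms since returning home from your trip". It records the duration of each symptom but no onset date.
- **First prompt** (footnote to Table 2, clinic events): "Study personnel will call the participant within 3 days of return from travel to remind participants to complete their web-based post-travel questionnaire".
- **Later calls** (Study Instruments, Post-travel): "Study personnel will make follow-up telephone calls on days 3, 5, 7, and 10 after return as needed". Appendix G gives all four the same purpose: "Reminder for post-travel questionnaire and stool sample submission".
- **Compliance and close-out:** the top grade of questionnaire compliance is "Full = participant completes all questionnaires", with no condition on timing. Under Outcomes, a participant's study period ends once all forms and specimens are in. The Study period definition lets submission run to "a maximum of 17 days post-travel".
- **On-trip capture:** the daily diary (Appendix D) covers trip days 1 to 21.
- **Unscheduled routes:** participants are told to contact the clinic about TD symptoms (Description of Risks to the Participant). Sick visits are possible (Laboratory Instruments). Table 2 lists adverse-event reporting up to day 10 after return.

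**The concern.** A form that asks about symptoms since return can only look back from the day it is answered. Day 10 is both the last on-time day and the end of the endpoint window, so an on-time form covers the whole window only if it is answered on day 10. The visible procedures encourage earlier answers, and once someone has submitted, nothing scheduled asks again.

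The gap is confined to participants who answer before day 10 and are TD-free when they answer. Those with on-trip TD are already cases through the diary, and those who answer on day 10 are fully covered. For the rest, the length of observation depends on when they happened to reply, and the plan does not say how the unobserved days are scored. Those days cannot be recovered afterwards.

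A smaller, related gap is the missing onset date. A form answered between day 11 and day 17 could count an episode that began after the window closed.

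**Working it through.** **The plan's own figure.** Sample Size and Power Calculation gives 40% against 0.40 - 0.40 x 0.30 = 28%, alpha 0.05 and 80% power. With a two-sided test and pooled variance:

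n per arm = [1.960 x sqrt(2 x 0.34 x 0.66) + 0.842 x sqrt(0.40 x 0.60 + 0.28 x 0.72)]^2 / 0.12^2 = 243.4, rounded up to 244, or 488 in total.

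This matches the stated 488, and power at 244 per arm is 80.1%. The point concerns ascertainment, not the sample-size arithmetic.

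**Assumed inputs.** The documents give none of the following:
- s, the share of full-window TD that starts after return: 10% to 25%.
- Onset over the 10 days: uniform, or clustered early (exponential, mean 3 days).
- The day d on which the form is answered.
- Whether the planned 40% refers to the full window or to the trip only.

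**Share c of post-return episodes seen by a form on day d.** Uniform: c = d/10. Clustered: c = (1 - exp(-d/3)) / (1 - exp(-10/3)).

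| Form day | Uniform | Clustered |
|---|---|---|
| 3 | 0.30 | 0.656 |
| 5 | 0.50 | 0.841 |
| 7 | 0.70 | 0.936 |
| 10 | 1 | 1 |
| A quarter of forms on each day | 0.625 | 0.858 |

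**Case A: 40% is full-window incidence, with equal protection throughout.** Both rates are multiplied by 1 - s(1 - c).
- Spread form days, uniform, s = 0.10: multiplier 0.9625, so 0.385 vs 0.270 and power 77.8%.
- Spread form days, uniform, s = 0.25: multiplier 0.906, so 0.3625 vs 0.254 and power 74.1%.
- Spread form days, clustered: 79.2% (s = 0.10) and 77.9% (s = 0.25).
- Extreme: everyone on day 3, uniform, s = 0.25: 0.330 vs 0.231 and power 68.3%.

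The risk ratio stays at 0.70 throughout. The planned odds ratio moves from 0.583 to at most 0.610, in the extreme case.

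**Case B: 40% is on-trip incidence, with equal protection throughout.** Observed rates are 0.40 and 0.28, each multiplied by 1 + cs/(1 - s). With day-3 forms and uniform onset:
- s = 0.10: 0.413 vs 0.289, power 82%.
- s = 0.25: 0.440 vs 0.308, power 86%.

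Even with no post-return capture (c = 0), the rates are the planned 0.40 and 0.28, so power does not fall below 80%.

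**Case C: 40% is full-window incidence and post-return TD is not reduced by BSS.** Dosing ceases on return, so this is possible, but the documents do not establish it. Observed placebo rate = 0.40(1 - s) + 0.40sc. Observed BSS rate = 0.28(1 - s) + 0.40sc. Full capture sets c = 1.

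| s | Full window: rates, RR, power | Day-3 forms, uniform: rates, RR, power | Protection overstated by |
|---|---|---|---|
| 0.10 | 0.400 vs 0.292, 0.730, 70.9% | 0.372 vs 0.264, 0.710, 72.8% | 2.0 points |
| 0.20 | 0.400 vs 0.304, 0.760, 60.3% | 0.344 vs 0.248, 0.721, 64.2% | 3.9 points |
| 0.25 | 0.400 vs 0.310, 0.775, 54.7% | 0.330 vs 0.240, 0.727, 59.6% | 4.8 points |

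With form days spread evenly and s = 0.25, the rates are 0.3625 vs 0.2725, RR 0.752, and the overstatement is 2.3 points. In Case C full capture lowers power, by 2 to 5 points in the table.

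**Cost of a missing-data rule.** Suppose early responders who skip a day-10 question were dropped as missing. Known cases stay in, so only non-cases leave. If 10%, 20% or 30% of non-cases drop out of each arm:
- 10%: 0.40/(0.40 + 0.60 x 0.9) = 0.426 vs 0.28/(0.28 + 0.72 x 0.9) = 0.302, RR 0.71.
- 20%: 0.455 vs 0.327, RR 0.72.
- 30%: 0.488 vs 0.357, RR 0.73.

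A complete-case rule would therefore move a true 0.70 towards 1, a distortion that Case A does not have.

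**The case against.** **Unseen appendices.** A send or completion day could well be set in Appendix J (the automatic e-mail) or Appendix K (the participant handout), and neither was available. This stands as a reason to check them first. It does not remove the point, because the main text itself prompts completion within 3 days of return.

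**Other routes.** Participants are asked to report TD symptoms, may attend a sick visit, and are covered by post-travel adverse-event reporting. These lessen the gap, but none is a scheduled question about TD, and no rule brings such reports into the endpoint.

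**Small effect of unknown sign.** Largely right. The power loss requires reading the 40% as full-window incidence, which the sample-size section does not say. The lowest figure also needs a 25% post-return share, uniform onset and day-3 forms from everyone.

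**Stronger readings that a reader might infer.** One is that the trial is underpowered; Case B shows that this does not follow. Another is that early forms bias the result in favour of BSS. That needs a different post-return effect or a different form day by arm. The documents give no data on the first, and nothing in them suggests the second in a blinded trial.

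**Conclusion.** The gap is real on the visible text: following the plan as written leaves part of the primary-endpoint window unobserved for TD-free early responders, and follow-up length then varies between participants. Its size and direction cannot be derived from the documents.

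The range runs from no loss against the planned power (Case B), through 74-79% power with an unchanged risk ratio (Case A, spread form days), to protection overstated by 2-5 points (Case C, day-3 forms, uniform onset). Every figure beyond 488 and 80% rests on the assumptions listed. This supports a cheap improvement to ascertainment. It does not support a claim that the sample size is wrong or that the comparison is biased in a known direction.

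**What to change.** Check Appendices J and K first. If they already fix completion on day 10, reconcile that with the day-3 prompt in the main text. Otherwise:

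1. Keep the current form and reminders. On day 10, send everyone who answered earlier one web question: have you had at least three loose stools within 24 hours since your earlier answers, and on what date did this start? Use the existing day-10 call slot for those who do not reply.
2. Add an onset date to the diarrhea item of Appendix E, question 1, so that answers given after day 10 count only onsets up to day 10.
3. Record the date on which each form is answered.
4. Keep participants who do not answer the day-10 question in the primary analysis, with the status observed up to their last answer. Do not drop them as missing, and state that not answering is not loss to follow-up, since loss to follow-up is a criterion for removal. Report a sensitivity analysis for their unobserved days.

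The cost is one short question, calls to non-responders in a slot that already exists, one extra field and a slightly later close-out. Power may be slightly lower if BSS does not reduce post-return TD (2-5 points in Case C), which is the price of measuring the endpoint as defined. No change to the sample size is needed.
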